7.1.2.6.5 Response in Non-measurable lesions (RECIST 1.1)

While some non-target lesions may actually be measurable, they need not be measured and instead should be assessed only qualitatively.

- Complete Response (CR): Disappearance of all non-target lesions and normalization of tumor marker level. All lymph nodes must be non-pathological in size (<10 mm short axis).
- Non-CR/Non-PD: Persistence of one or more non-target lesion(s) and/or maintenance of tumor marker level above the normal limits.
- Progressive Disease (PD): Unequivocal progression of existing non-target lesions. (Note: the appearance of one or more new lesions is also considered progression).

When the subject also has measurable disease, to achieve 'unequivocal progression' on the basis of non-target disease, there must be an overall level of substantial worsening in non-target disease such that, even in presence of SD or PR in target disease, the overall tumor burden has increased sufficiently to merit discontinuation of therapy.

In the event that the subject has only non-measurable disease, the same general concepts apply as noted above, however, in this instance there is no measurable disease assessment to factor into the interpretation of an increase in non-measurable disease burden. Because worsening in non-target disease cannot be easily quantified, a useful test that can be applied when assessing subjects for unequivocal progression is to consider if the increase in overall disease burden based on the change in non-measurable disease is comparable in magnitude to the increase that would be required to declare PD for measurable disease: (i.e., an increase in tumor burden representing an additional 73% increase in ‘volume’ which is equivalent to a 20% increase diameter in a measurable lesion).

7.1.2.6.6 Immune-Related Response in Non-measurable Lesions

At each tumor assessment, the presence of any new, non-measurable lesions is assessed. The presence of such lesions will rule out an overall response of irCR. An increase in the size or number of new, non-measurable lesions does not necessarily imply an overall response of irPD; if these lesions become measurable (≥ 10 mm) at a subsequent tumor assessment, their measurement will at that point start to contribute to the TMTB.

In addition, the response in non-target lesions is defined as follows:

- Complete Response (irCR): complete disappearance of all non-target lesions
- Stable Disease (irSD): non-target lesions are stable
- Progressive Disease (irPD): unequivocal increases in number or size of non-target lesions. To achieve unequivocal progression of non-target lesions, there must be an overall level of substantial worsening of non-target disease that is of a magnitude that the treating physician would feel it is important to change therapy

NOTE: Equivocal findings of progression of non-target lesions (e.g., small and uncertain new lesions; cystic changes or necrosis in existing lesions) should be considered irSD, and treatment may continue until the next scheduled assessment.

7.1.2.6.7 Overall Response

Overall response will be determined based on RECIST 1.1 criteria and by irRECIST criteria. The differences are noted below in [Table 12](#). Overall response according to irRECIST is derived from the responses in measurable lesions (based on TMTB) and the presence of any non-measurable lesions.

Table 12 Tumor Response Evaluation: Comparison of RECIST 1.1 and irRECIST

Criteria	RECIST1.1	irRECIST
New measurable lesions (≥ 10 mm)	Always represents PD	Incorporated into tumor burden

New non-measurable lesions (< 10 mm)	Always represents PD	Does not define progression but precludes irCR
Non-Target lesions	Changes contribute to defining BOR of CR, PR, SD, and PD	Contribute to defining irCR (complete disappearance required)
CR	Disappearance of all lesions	Disappearance of all lesions
PR	≥ 30% decrease in the sum of the longest diameter of all target lesions compared with baseline, in absence of new lesions or unequivocal progression of non-target lesions	≥ 30% decrease in tumor burden compared with baseline
SD	Neither sufficient shrinkage to qualify for PR nor sufficient increase to qualify for PD, taking as reference the smallest sum diameters while on study	Neither a 30% decrease in tumor burden compared with baseline nor a 20% increase compared with nadir can be established
PD	At least 20% increase in sum of diameters of target lesions, taking as reference the smallest sum on study. In addition to the relative increase of 20%, the sum must also demonstrate an absolute increase of at least 5mm. The appearance of one or more new lesions is also considered progression.	At least 20% increase in tumor burden compared with nadir (at any single time point) ^a

irRECIST = immune-related Response Evaluation Criteria in Solid Tumors; BOR = best overall response; CR = complete response; irCR = immune-related complete response; PD = progressive disease; PR = partial response; SD = stable disease;

^a Subjects with an initial finding of progressive disease (irPD) before or at the 12-week imaging assessment, but without rapid clinical deterioration, require confirmation of irPD with a second, consecutive scan obtained ≥ 4 weeks from the initiation documentation. Subjects will continue to receive study treatment until irPD is confirmed at this later time point. BOR will therefore include responses occurring at any time before disease progression and after early progression (i.e., within the first 12 weeks of the study).

7.1.2.6.8 Best Overall Response (RECIST 1.1)

The best overall response is the best response recorded from the start of the study treatment until the end of treatment taking into account any requirement for confirmation. The subject's best overall response assignment will depend on the findings of both target and non-target disease and will also take into consideration the appearance of new lesions [Table 13](#).

Table 13 Best Overall Response (RECIST 1.1)

Target Lesions		Non-Target Lesions		Overall Response
Baseline (Index) and New Measurable Lesions		Baseline Lesions	Unequivocal New Lesions	
CR	CR	CR	No	CR

Target Lesions		Non-Target Lesions		
Baseline (Index) and New Measurable Lesions		Baseline Lesions	Uequivocal New Lesions	Overall Response
CR	Non-CR/Non-PD		No	PR
CR	NE		No	PR
PR	Non-PD or NE		No	PR
SD	Non-PD or NE		No	SD
Not all evaluated	Non-PD		No	NE
PD	Any		Yes or No	PD
Any	PD		Yes or No	PD
Any	Any		Yes	PD

The immune-related best overall response (irBOR) is the best irCR overall response over the study as a whole, recorded between the date of first dose until the last TA prior to subsequent therapy (including tumor resection surgery) for the individual subject in the study (Table 14). As with the primary definitions of tumor response, early progression (i.e., irPD occurring prior to Week 12) will not preclude an irBOR of irCR, irPR or irSD resulting from the Week 12 assessment. An assessment of irPD at or after Week 12 will preclude a subsequent irBOR of irCR, irPR or irSD. However, any post-progression clinical activity in subjects with irBOR of irPD may be summarized for exploratory purposes.

Table 14 Immune-Related Best Overall Response (irBOR)

Target Lesions Baseline (Index) and New Measurable Lesions		Non-Target Lesions ^a		
Total Measurable Tumor Burden (TMTB)		Baseline Lesions	Uequivocal New Lesions	irRC Overall Response
irCR	irCR		No	irCR
irCR	irSD		No	irPR
irPR	irCR or irSD		No	irPR
irSD	irCR or irSD		No	irSD
irPD	Any		Yes or No	irPD
Any	Uequivocal Progression		Yes or No	irPD

Target Lesions Baseline (Index) and New Measurable Lesions		Non-Target Lesions ^a	
Total Measurable Tumor Burden (TMTB)		Baseline Lesions	Uequivocal New Lesions
Any	Any	Yes	irPD

irCR = immune-related complete response; irPR = immune-related partial response; irSD = immune-related stable disease; irPD = immune-related progressive disease

^a Any increase in the size or number of non-measurable lesions does not necessarily imply an overall response of irPD. If these lesions become measurable (≥ 10 mm) at a subsequent assessment, their measurement will at that point start to contribute to the total measurable tumor burden. To achieve unequivocal progression of non-target lesions, there must be substantial worsening in non-target disease that is of a magnitude that the investigator feels it is important to change therapy. Equivocal findings of progression of non-target lesions (e.g., small and uncertain new lesions; cystic changes or necrosis in existing lesions) should be considered irSD, and treatment may continue until the next assessment.

[figure not shown]

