7.1.2.6.4 Immune-Related Response in Measurable Lesions (irRECIST)

In addition to evaluation using RECIST 1.1 criteria, an immune response adaptation of RECIST will be applied to this trial. The essential differences between irRECIST and RECIST criteria are as follows:

- New measurable lesions do not necessarily constitute progressive disease and they should be added into the total tumor burden. New non-measurable lesions do not constitute disease progression but will prevent the determination of an irCR.
- Subjects with an initial finding of progressive disease (irPD) before or at the 12-week imaging assessment, but without rapid clinical deterioration, require confirmation of irPD with a second, consecutive scan obtained ≥ 4 weeks from the

initiation documentation. Subjects will continue to receive study treatment until irPD is confirmed at this later time point.

At baseline, the sum of the longest diameters (SumD) of all target lesions (up to 2 per organ and 5 in total) is measured. At each subsequent tumor assessment, the SumD of the target lesions and of new, measurable lesions (≥ 10 mm [lymph nodes ≥ 15 mm in shortest diameter]; up to 2 new lesions per organ, total 5 new lesions) are added together to provide the total measurable tumor burden (TMTB):

$$\text{TMTB} = \text{SumD target lesions} + \text{SumD new, measurable lesions}$$

Percentage changes in TMTB per assessment timepoint describe the size and growth kinetics of both old and new measurable lesions as they appear. At each tumor assessment, the response in target and new measurable lesions is defined based on the change in TMTB (after ruling out irPD) as follows:

- Complete Response (irCR): complete disappearance of all target and new, measurable lesions, with the exceptions of lymph nodes which must decrease to <10 mm in short axis
- Partial Response (irPR): decrease in TMTB $\geq 30\%$ relative to baseline (see below)
- Stable Disease (irSD): not meeting criteria for irCR or irPR, in absence of irPD
- Progressive Disease (irPD): increase in TMTB $\geq 20\%$ relative to nadir

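### An irPD first found at the 12-week assessment is provisional in 7.1.2.6.4 and Table 12 but final in the irBOR paragraph, so irBOR is ambiguous when the repeat scan does not confirm it

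*Combined protocol and SAP*

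**What the plan says.** Three places in the protocol govern how an early irPD feeds into best response.

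- **7.1.2.6.4 (irRECIST, measurable lesions):** "Subjects with an initial finding of progressive disease (irPD) before or at the 12-week imaging assessment, but without rapid clinical deterioration, require confirmation". The confirming scan comes at least 4 weeks after irPD is first seen.
- **Table 12, footnote a (7.1.2.6.7):** repeats that boundary and draws the consequence for the endpoint: "BOR will therefore include responses occurring at any time before disease progression and after early progression (i.e., within the first 12 weeks of the study".
- **irBOR paragraph (in 7.1.2.6.8, ahead of Table 14):** says that "early progression (i.e., irPD occurring prior to Week 12) will not preclude an irBOR of irCR, irPR or irSD resulting from the Week 12 assessment", and then: "An assessment of irPD at or after Week 12 will preclude a subsequent irBOR of irCR, irPR or irSD". It introduces this as following the primary response definitions. Its last sentence allows activity after progression to be summarised as exploratory.

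Other relevant text:

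- 7.1.5.2 puts the first on-treatment scan at Week 10 (±1 week), then every 12 weeks. Note 10 of the Part A flow chart also gives Week 10 for the first cycle.
- The tumor imaging row of the Part B flow chart (6.2), as extracted, appears to carry a mark under both Wk 10 and Wk 12.
- 7.1.2.6.9 asks for a repeat assessment at least 4 weeks later to confirm PD, with no 12-week limit.

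**The concern.** An irPD first recorded at the 12-week assessment falls on opposite sides of the boundary. Two places class it as early and subject to confirmation. The irBOR paragraph classes it as late and closes the subject as irPD before the required repeat scan has been read. No text says which rule prevails.

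irRECIST is used here so that initial growth followed by shrinkage is not automatically scored as failure. Section 3.2 says the anti-tumor activity results, including irRECIST, are meant to guide the design of a later randomised study. If the boundary is left open, a subject with this pattern is classified by whichever paragraph is programmed. Because the trial is open-label, that choice could be made after the individual outcomes are known.

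**Working it through.** The plan states no sample-size, power or alpha figure for this endpoint, so there is nothing of that kind to reproduce. The check applies each rule to the same hypothetical subject.

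**Inputs from the documents**
- irPR: total measurable tumor burden (TMTB) at least 30% below baseline; irPD: at least 20% above nadir (7.1.2.6.4).
- Repeat scan at least 4 weeks after the first irPD (7.1.2.6.4, Table 12 footnote a).
- About 30 subjects planned at the combination RP2D (5.2.1.1.3); about 51 in the trial (section 1).

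**Assumed for illustration:** baseline TMTB 100 mm, no earlier response, no rapid deterioration, first irPD at 130 mm, repeat scan 4 weeks later at 65, 90 or 150 mm.

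**Rule A** (7.1.2.6.4 and footnote a): irPD at Week 12 or earlier is provisional until the repeat scan. irPD after Week 12 is taken as final, because these two places require confirmation only up to Week 12.

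**Rule B** (irBOR paragraph): irPD before Week 12 is not final; irPD at or after Week 12 is.

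**Changes**
- First irPD: 130/100 − 1 = +30%, so irPD.
- Repeat at 65 mm: 65/100 − 1 = −35%, so irPR.
- Repeat at 90 mm: 90/100 − 1 = −10%, so irSD.
- Repeat at 150 mm: 150/100 − 1 = +50% over the nadir of 100 mm, so irPD is confirmed.

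| First irPD at | Repeat scan | Rule A | Rule B |
|---|---|---|---|
| Week 10 or 11 | irPR / irSD / irPD | irPR / irSD / irPD | irPR / irSD / irPD |
| **Week 12** | **irPR** | **irPR** | **irPD** |
| **Week 12** | **irSD** | **irSD** | **irPD** |
| Week 12 | irPD | irPD | irPD |
| Week 13, 22 or 24 | any | irPD | irPD |

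The rules split in one situation only: irPD first found at Week 12 and not confirmed. An irCR on the repeat scan would split in the same way.

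**Size per subject.** 8.2.4 defines response rate as CRs plus PRs over treated subjects and does not say whether irCR and irPR count. If they do, each reclassified irPR moves the rate by 1/30 = 3.3 points at the RP2D, or 1/51 = 2.0 points over all subjects. For scale, 1/30 is 3.3% (exact 95% interval 0.1 to 17.2) and 2/30 is 6.7% (0.8 to 22.1). A subject reclassified to irSD does not change the response rate. Duration of response in 8.2.4 does use irCR and irPR, so whether a reclassified responder enters that summary also depends on the rule.

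**The case against.** The strongest objection is the schedule. On the written text the first on-treatment scan falls in Weeks 9 to 11 and the next near Week 22, and the table above shows the rules agreeing at those weeks. The apparent Wk 12 mark in the Part B flow chart rests on column positions in an extracted table and might denote the later 12-weekly scans. This limits how often the conflict arises but does not remove it. All three rules refer to a 12-week or Week 12 assessment, none ties it to the Week 10 scan, and 7.1 permits unscheduled procedures. If a programmer labels the first scan as the 12-week assessment, every unconfirmed irPD on that scan is affected. If calendar weeks are used and the schedule is kept, perhaps none is.

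It can also be said that the irBOR paragraph means confirmed irPD. That reading would remove the conflict, but the paragraph does not say so, and its preceding sentence uses irPD for a finding that can be overturned.

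Third, the analysis is descriptive (8.1), RECIST 1.1 response is assessed separately, and activity after progression may still be summarised as exploratory. All of this stands and limits the consequence. An optional exploratory summary does not settle how irBOR itself is scored.

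A reader might go further and infer that every 12-week irPD is scored in opposite ways. It is not: when the repeat scan confirms progression, both rules give irPD. A reader might also infer a shift of several subjects and up to 10 points in the response rate. The documents give no basis for any such count.

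**Conclusion.** The conflict is real and is in the current text, but it is narrow. It affects irBOR only for a subject without rapid deterioration whose irPD is first found at the 12-week assessment and is not confirmed at least 4 weeks later. irBOR is then irCR, irPR or irSD under 7.1.2.6.4 and Table 12 footnote a, and irPD under the irBOR paragraph.

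The number of such subjects is unknown and may be small or zero, depending on which scan is meant by the 12-week assessment. The effect is 3.3 points per reclassified irPR at the RP2D, assuming 30 subjects and that immune-related responses enter the rate. That is small beside the sampling uncertainty with 30 subjects, and no formal decision in the plan rests on it. It is still worth settling before irBOR is derived, because the correction is cheap and the choice should not be made with outcomes in view.

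**What to change.** For endpoint derivation only, align the irBOR paragraph with 7.1.2.6.4 and Table 12 footnote a. Suggested wording: *An irPD first recorded no later than the 12-week assessment, in a subject without rapid clinical deterioration, does not rule out a later irBOR of irCR, irPR or irSD if the repeat scan at least 4 weeks later does not confirm it. A confirmed irPD does rule these out.*

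The same amendment should state:

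1. How an early irPD is scored when the subject deteriorates rapidly or has no repeat scan.
2. Which scheduled scan, Week 10 or Week 12, is the 12-week assessment, with the Part B flow chart made to agree.
3. How an irPD first seen after that assessment is scored, reconciled with the repeat-scan text in 7.1.2.6.9, which has no 12-week limit.
4. Whether irCR and irPR enter the response rate in 8.2.4.

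The cost is a few sentences and the matching derivation. Aligning the early-irPD rule adds no scans, because 7.1.2.6.4 already requires the repeat scan. Rules on continuing or stopping treatment are outside this change and remain with the sponsor.

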7.1.2.6.9 Treatment after Initial Evidence of Radiologic Disease Progression

Immunotherapy may produce antitumor effects by potentiating endogenous cancer-specific immune response. The response patterns seen with such an approach may extend beyond the typical time course of responses seen with cytotoxic agents and can manifest as a clinical response after an initial increase on tumor burden or even the appearance of new lesions. If radiological imaging shows progressive disease (PD), subjects may continue on study with the option of continuing treatment, provided there is:

- No deterioration in ECOG performance status
- Absence of signs and symptoms (including worsening of laboratory values) indicating disease progression
- Absence of rapid progression of disease
- Absence of progressive tumor at critical anatomical sites (e.g., cord compression) requiring urgent alternative medical intervention

Tumor assessment should be repeated ≥ 4 weeks later to confirm PD. If repeat imaging shows a reduction in the tumor burden demonstrating CR, partial response (PR) or stable disease (SD) compared to the initial scan, treatments may be continued or resumed. If repeat imaging shows continued progression of disease, subjects will be discontinued from study therapy, unless the basis for the PD assessment is enlarged tumor-draining lymph nodes in the presence of a target tumor reduction. In determining whether or not tumor burden has increased or decreased, Investigators should consider all target lesions as well as non-target lesions. If the repeat imaging confirms initially documented PD but shows no evidence of further tumor progression, subjects should be discontinued from the study treatment.

7.1.2.7 Correlative Studies Blood Sampling

7.1.3 Laboratory Procedures/Assessments

Details regarding specific laboratory procedures/assessments to be performed in this trial are provided below.

7.1.3.1 Laboratory Safety Evaluations (Hematology and Chemistry)

Laboratory tests for hematology, chemistry, and others are specified in [Table 15](#). The total amount of blood to be drawn over the course of the trial (from pre-trial to post-trial visits), including approximate blood by visit and by sample type per subject can be found in the Procedures Manual.

Table 15 Laboratory Tests

Hematology	Chemistry	Other
Hematocrit	Albumin	PT (INR) (screening only)
Hemoglobin	Alkaline phosphatase	aPTT (screening only)
Platelet count	Alanine aminotransferase (ALT)	Total triiodothyronine (T3)
WBC (total and differential)	Aspartate aminotransferase (AST)	Free thyroxine (T4)
Red Blood Cell Count	Lactate dehydrogenase (LDH)	Thyroid stimulating hormone (TSH)
Absolute Neutrophil Count	Carbon Dioxide (CO ₂ or bicarbonate)	
	Calcium	Serum creatinine OR creatinine clearance
	Chloride	Blood for correlative studies
	Creatinine	
	Glucose	
	Potassium	
	Sodium	
	Total Bilirubin	
	Direct Bilirubin (If total bilirubin is above the upper limit of normal)	

Hematology	Chemistry	Other
	Total protein	
	Blood Urea Nitrogen	
	Erythrocyte Sedimentation Rate*	
	C-Reactive Protein*	

Laboratory tests should be performed within 3 days prior to dosing. Results must be reviewed by the Investigator or qualified designee and found to be acceptable per Inclusion Criteria (Refer to [Table 3](#)) prior to each dose of trial treatment.

* *Lm* Surveillance Monitoring will include routine monitoring of CBC, CMP (including CRP, ESR) and blood cultures. Following completion of study treatment or at the time of study discontinuation, if earlier, testing will be performed on all subjects who have received at least one dose of ADXS31-142. It will occur every 3 months (+ 2 weeks) for 3 years beginning 3 months after the last dose of study treatment. CRP, ESR, and blood cultures are only collected during the *Lm* Surveillance Monitoring period, and not during the main part of the study. Lactate dehydrogenase (LDH) is only collected during the main part of the study, and is not collected during the *Lm* Surveillance Monitoring period (it is not part of the standard CMP).

